12 OBJECTIVES

12.1 Primary safety Objective

• To compare the safety of AP1189 against placebo by evaluating AEs, SAEs, and laboratory abnormalities.

12.2 Primary efficacy Objective

 Effect of AP1189 vs. placebo in subjects with severe active RA (CDAI > 22), undergoing up-titration with MTX, by showing a change in CDAI from severe (CDAI > 22) to moderate (CDAI ≤ 22) after 4 weeks treatment compared to baseline.

12.3 Secondary efficacy Objectives

To compare the effects of AP1189 against placebo by assessing:

- Proportion of subjects achieving a reduction of more than 10 (ten) swollen and/or tender joints at week
 4 compared to baseline
- Proportion of subjects achieving a change in CDAI score at week 4 compared to baseline
 - o Proportion of subjects with a 5-point decrease
 - o Proportion of subjects with a 10-point decrease
 - o Proportion of subjects with a 15-point decrease
- Proportion of subjects achieving a change in value to ≤ 3.2 as measured by DAS28 at week 4 compared to baseline
- Change in subject-reported HAQ-DI at week 4 compared to baseline
- Change in subject-reported fatigue using FACIT-Fatigue at week 4 compared to baseline
- Proportion of subjects achieving American College of Rheumatology (ACR) response assessed by ACR20, ACR50, and ACR70

12.4 Tertiary Efficacy Objectives

Effect of AP1189 compared to placebo at week 4 compared to baseline on inflammatory and collagen destructive biomarkers. The biomarkers include:

- CXCL13
- IL-1β
- IL-6
- IL-10 and TNF- α

Protocol Code Number: SynAct-CS002

12.4.1 Arthroscopy sub-Study

Effect of AP1189 compared to placebo on joint structures and inflammation as assessed by synovial biopsy at baseline and after 4 weeks treatment (only Part 2 at selected sites).

13 SAFETY ENDPOINTS

13.1 Primary Safety Endpoint

The safety of AP1189 against placebo by evaluating adverse events (AEs), serious adverse events (SAEs), and laboratory abnormalities.

14 EFFICACY ENDPOINTS

14.1 Primary Efficacy Endpoint

The change in CDAI after 4 weeks of treatment compared to baseline will be evaluated by assessing the following, by treatment group:

- Mean change in CDAI from baseline to week 4
- Proportion of subjects with a change in CDAI score from severe (CDAI > 22) to moderate (CDAI ≤ 22) at week 4 compared to baseline.

14.2 Secondary Efficacy Endpoints

The effects of AP1189 against placebo will be evaluated by assessing the following by treatment group:

- Proportion of subjects achieving a reduction of more than 10 (ten) swollen and/or tender joints (SJC and TJC, summarized) at week 4 compared to baseline
- Proportion of subjects achieving a change in CDAI score at week 4 compared to baseline
 - Proportion of subjects with a 5-point decrease
 - Proportion of subjects with a 10-point decrease
 - o Proportion of subjects with a 15-point decrease
- Proportion of subjects achieving a change in DAS28 from DAS28 >3.2 to DAS28 ≤ 3.2 at week 4 compared
 to baseline
- Change of HAQ-DI at week 4 compared to baseline
- Change of FACIT-Fatigue at week 4 compared to baseline
- Proportion of subjects achieving ACR response assessed by ACR 20, ACR 50, and AC70

14.3 Tertiary Efficacy Endpoints

The effect of AP1189 compared to placebo at week 4 compared to baseline will be further evaluated by assessing the following by treatment group:

- CXCL13, IL-1β, IL-6, IL-10, and TNF-α
- Synovial biopsy at baseline and after 4 weeks treatment (only Part 2 at selected sites).

[figure not shown]
Protocol Code Number: SynAct-CS002

15 EXPERIMENTAL PLAN

15.1 Study Design

This study is a multicenter, two-part, randomized, double-blind, placebo-controlled, 4-week study with repeated doses of AP1189. The study population will consist of newly diagnosed subjects with severe active RA (CDAI > 22) who are to start up-titration with MTX. A minimum of 90 subjects are expected to complete the study, plus 45 subjects from Bulgaria and/or Moldova for a sub-study (see Section 15.2). Up to 120 subjects are planned to be enrolled for the main study to account for discontinuation rate, and up to 60 subjects for the sub-study. The rationale for the number of subjects required is outlined in the section on sample size determination. The below Figure 1 shows the general study design.

Figure 1.: General study design (Part 1 and 2)

15.2 Sub-study of subjects from Bulgaria/Moldova

As Bulgaria and Moldova did not participate in Part 1 of the study, a sub-study has been added to investigate the effect in these two countries separately. In addition to analyzing the main study and the sub-study separately, all data will be pooled to investigate the overall effect in all participating countries.

15.3 Part 1 (main study only)

Following a successful screening evaluation, subjects who fulfill the enrollment criteria will be randomized in a 2:1 ratio in group A and B. One group will receive active treatment, and the other group will receive a placebo. Before randomization into group C/D (the same 2:1 ratio between active and placebo), the SC will look at blinded safety data from group A/B.

- Group A (min. 8 subjects): AP1189 dose 50 mg, once daily for 4 weeks (28 days) plus MTX (10-25 mg) weekly
- Group B (min. 4 subjects): placebo for 4 weeks (28 days) plus MTX (10-25 mg) weekly

SC Meeting

- Group C (min. 8 subjects): AP1189 dose 100 mg, once daily for 4 weeks (28 days) plus MTX (10-25 mg) weekly
- Group D (min. 4 subjects): placebo for 4 weeks (28 days) plus MTX (10-25 mg) weekly

Protocol Code Number: SynAct-CS002

15.3.1 Number of Subjects in Part 1

A minimum of 24 subjects is expected to complete Part 1 of the study. About 32 subjects are planned to be enrolled in accounting for discontinuation rate.

The rationale for the number of subjects required is outlined in the section on sample size determination.

15.4 Part 2

All subjects will be randomized into one design only, either design 1, 2, or 3 based on data from the interim analysis:

- Design 1: AP1189 dose 50 mg (min. 44 subjects) or placebo (min. 22 subjects), once daily for 4 weeks (28 days) plus MTX (10-25 mg) weekly
- Design 2: AP1189 dose 100 mg (min. 44 subjects) or placebo (min. 22 subjects), once daily for 4 weeks (28 days) plus MTX (10-25 mg) weekly
- Design 3: Continue with the same doses as in Part 1, in a 1:1:1 ratio (AP1189 50 mg (min. 22 subjects), AP1189 100 mg (min. 22 subjects) or placebo (min. 22 subjects)) plus MTX (10-25 mg) weekly

Following a successful screening evaluation, subjects who fulfill the enrollment criteria will be randomized accordingly.

15.4.1 Number of Subjects in Part 2

A minimum of 66 subjects in the main study is expected to complete Part 2 of the study, and 45 subjects in the sub-study. About 88 subjects are planned to be enrolled in the main study in accounting for discontinuation rate, and about 60 subjects in the sub-study.

The rationale for the number of subjects required is outlined in the section on sample size determination.

15.5 Estimated Study Duration

Total study duration is 18 months, and the study duration for each subject is approximately and up to 10 weeks.

15.6 Number of Investigational Sites

The study is to be conducted at sites in Europe and Moldova.

15.7 Visits during the Study

Subjects will have the following study visits: A Screening Visit (up to 2 weeks prior to baseline), a Baseline Visit (Day 0 visit), four visits during the treatment period (week 1, 2, 3 and 4) and the Follow Up Visit seven days after administration of the last study drug. Investigator or study nurse will make an End of Study (EOS) follow-up call to the subject four weeks after the subject took the last IMP to follow-up on outstanding safety issues (AE/ SAE). The study procedures for each visit are outlined in section 20.

15.8 Steering Committee (SC)

The SC is appointed by the sponsor and comprises of the coordinating investigators in Denmark, Sweden and Norway and a sponsor medical responsible person.

All decisions made by the SC will be documented and signed by its members as per the SC Charter (a specific charter will be developed to define roles and responsibilities).

Protocol Code Number: SynAct-CS002

The SC will review blinded laboratory data from the first min. 12 subjects randomized into group A or B before the next min. 12 subjects in Part I, group C/D can be included and randomized.

The SC will, based on the recommendations from the data monitoring committee (DMC), decide the design for Part 2. The SC will meet ad hoc.

15.9 Data Monitoring Committee (DMC)

The DMC is established by the sponsor and consists of a group of three study independent members: two independent external experts (a rheumatologist and a professor and specialist in hepatology and clinical pharmacology at Bispebjerg hospital), and an independent external statistician. A specific DMC charter will be developed to define roles and responsibilities.

The DMC will review the unblinded data from the interim analysis of the first min. 24 subjects from Part 1. The DMC will recommend a study design for Part 2 to the SC based on these data. All recommendations will be documented and signed by the DMC members, and they will provide a summary of the safety and tolerability data obtained in Part 1 and their design recommendation for Part 2.

The independent external statistician will analyze data for the interim analysis, following the procedure described in the statistical analysis plan and the protocol. The DMC will hereafter meet ad hoc as appropriate.

15.10 Criteria for Choice of Design for Part 2

The criteria for the choice of design 1, 2, or 3 for Part 2 are:

Design 1: AP1189 dose 50 mg (min. 44 subjects) or placebo (min. 22 subjects) plus MTX (10-25 mg) will be applied if:

- The efficacy, evaluated on the number of subjects showing reduced clinical score as defined in the protocol, is higher in the 50 mg group than in the 100 mg group.
- The safety profile of group A and B (50 mg AP1189 or placebo) is superior to the safety profile of group C and D (100 mg AP1189 or placebo).
 - The safety evaluation will focus on the number and the severity of the reported AEs and SAEs, on any laboratory findings with particular emphasis on liver and thyroid gland parameters, as well as vital signs.

Design 2: AP1189 dose 100 mg (min. 44 subjects) or placebo (min. 22 subjects) plus MTX (10-25 mg) will be applied if:

- The efficacy, evaluated on the number of subjects showing reduced clinical score as defined in the protocol, is higher in the 100 mg group than in the 50 mg group.
- The safety profile of group C and D (100 mg AP1189 or placebo) is superior or comparable to the safety profile of group A and B (50 mg AP1189 or placebo).
 - The safety evaluation will focus on the number and the severity of the reported AEs and SAEs, on any laboratory findings with particular emphasis on liver and thyroid gland parameters, as well as vital signs.

Protocol Code Number: SynAct-CS002

Design 3: Continue with the same doses as in Part 1, in a 1:1:1 ratio (AP1189 50 mg (min. 22 subjects), AP1189 100 mg (min. 22 subjects) or placebo (min. 22 subjects)) plus MTX (10-25 mg) will be applied if:

- The evaluation shows comparable safety profiles and comparable efficacy, evaluated on the number of subjects showing reduced clinical score as defined in the protocol, in the 50 and 100 mg groups.
- The safety evaluation will focus on the number and the severity of the reported AE and SAE, on any laboratory findings with particular emphasis on liver and thyroid gland parameters, as well as vital signs.

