## 3.7 Interim Analysis

An interim analysis has been performed, evaluating the first (minimum) 24 subjects from Part 1 of the trial in order to assess the safety and efficacy of the investigational product before proceeding to Part 2. Version 1 of this analysis plan was used for the interim analysis.

All safety parameters (ECG, vital signs, AEs/SAEs, laboratory abnormalities, etc.) and efficacy data for the primary efficacy endpoint were summarized by treatment and time point for the subjects included in Part 1 of the study, i.e., the following tables (see Appendix 4 for details) were presented (any MedDRA coding of AEs will not be performed for the interim):

• Table 11.4.1.3 (CDAI score)

Study SynAct-CS002 – Statistical Analysis Plan

- Table 11.4.1.4 (CDAI score, change from baseline to week 4)
- $\circ~$  Table 11.4.1.5 (CDAI score, change from severe (CDAI > 22) to moderate (CDAI  $\leq$  22) at week 4 compared to baseline)
- Table 12.2.1.1 to Table 12.5.5.1 (all safety tables).

Listings showing the following data were also presented:

- Patient disposition (including end of study information), i.e., the following listings (see Appendix 4 for details):
  - Listing 6.4.1 (Visit Registration)
  - Listing 6.4.2 (Informed Consent, Randomization, Subject Summary)
  - Listing 6.4.3 (Alcohol Consumption)
  - Listing 16.2.8.1 TB and Serology Tests)
  - Listing 6.4.10 (Inclusion Exclusion Criteria)
- Demographics and baseline characteristics, i.e. the following listings (see Appendix 4 for details):
  - Listing 16.2.4.1 (Demographics)
  - Listing 6.4.5 (Vital Signs)
  - Listing 16.2.4.3 (Age)
- Safety profiles (laboratory values, adverse events, related adverse events, serious adverse events (SAE), adverse events leading to withdrawal), i.e., the following listings (see Appendix 4 for details):
  - Listing 16.2.8.2 (Blood Biochemistry)
  - Listing 16.2.8.3 (Blood Haematology)
  - Listing 16.2.7.1 (Adverse Event Q).
- Efficacy data for the primary study endpoint
  - Listing 16.2.6.3 (CDAI)
  - Listing 16.2.6.7 (Changes from baseline in CDAI)

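### The Part 2 design rule compares counts of improved subjects between two dose groups whose sizes are not tied together, so unequal groups would favour the larger one; it should compare proportions

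*Protocol*

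**What the plan says.** Protocol section 15.10 gives one efficacy criterion for each Part 2 design.

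- Design 1 (50 mg) applies if the efficacy result, "evaluated on the number of subjects showing reduced clinical score as defined in the protocol, is higher in the 50 mg group" when set against the other dose.
- Design 2 (100 mg) applies if the same count "is higher in the 100 mg group than in the 50 mg group".
- Design 3 (both doses) applies if there is "comparable efficacy, evaluated on the number of subjects showing reduced clinical score as defined in the protocol, in the 50 and 100 mg groups", with comparable safety.

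Designs 1 and 2 each carry a safety condition as well. No denominator, margin or tie rule is stated.

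Section 15.3 sets the group sizes as minimums: "Group A (min. 8 subjects): AP1189 dose 50 mg" and "Group C (min. 8 subjects): AP1189 dose 100 mg". The second cohort is randomized only after the Steering Committee has reviewed blinded data from the first. Section 15.3.1 expects at least 24 completers and adds: "About 32 subjects are planned to be enrolled in accounting for discontinuation rate". It does not say how the 32 divide between cohorts. Section 16.5.1 says subjects who discontinue are not replaced, and SAP section 3.3 leaves subjects with a missing value out of any analysis that needs it, without imputation.

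The primary efficacy endpoint in protocol sections 14.1 and 23.5.1 includes a proportion, not a count: subjects moving from CDAI > 22 to CDAI ≤ 22 at week 4. SAP section 3.7 (version 2.0) states that the interim analysis has already been performed, and refers to the DMC charter for the design criteria.

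**The concern.** A count ranks two groups fairly only when they have the same number of evaluable subjects. The two doses are not randomized against each other. Each cohort has a floor but no ceiling, and losses before week 4 are neither replaced nor imputed. Even equal enrolment can therefore leave unequal numbers with a week-4 CDAI. On a raw count, every extra subject is one more chance of a responder, so group size, which says nothing about treatment effect, enters the choice of dose for Part 2. A simple case: 5 of 8 (62.5%) loses to 6 of 12 (50%).

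**Working it through.** **Group sizes.** The stated minimum reproduces: 8 + 4 + 8 + 4 = 24. With 2:1 allocation and an even split, 32 enrolled gives 32 × 2/3 ÷ 2 = 10.7 active subjects per cohort. I therefore examined active groups from 8 to 11. The documents set no upper limit.

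**Responder rates.** The documents give none and state no operating characteristics for the rule. All rates below are assumptions.

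**Method.** Let X and Y be the numbers improved in the smaller group (size m, rate p) and the larger group (size n, rate q), as independent binomials. The count rule favours the larger group with probability P(Y > X) = Σ P(X = x) · P(Y > x), summed over x = 0 to m. The proportion rule compares X/m with Y/n. Any lead counts as higher. Results are exact, in per cent.

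| Smaller vs larger | True rates | Counts: smaller / larger / tie | Proportions: smaller / larger / tie |
|---|---|---|---|
| 8 vs 8 | 40 / 40 | 40.0 / 40.0 / 20.1 | same |
| 8 vs 9 | 50 / 50 | 31.5 / 50.0 / 18.5 | 50.0 / 50.0 / 0 |
| 8 vs 11 | 40 / 40 | 21.3 / 62.7 / 15.9 | 51.2 / 48.8 / 0 |
| 8 vs 8 | 50 / 40 | 56.3 / 25.5 / 18.2 | same |
| 8 vs 9 | 50 / 40 | 48.4 / 32.8 / 18.8 | 67.2 / 32.8 / 0 |
| 8 vs 10 | 50 / 40 | 40.9 / 40.3 / 18.8 | 62.6 / 31.9 / 5.5 |
| 10 vs 11 | 50 / 40 | 52.1 / 31.2 / 16.7 | 68.8 / 31.2 / 0 |
| 8 vs 11 | 50 / 40 | 34.1 / 47.8 / 18.1 | 67.7 / 32.3 / 0 |
| 11 vs 11 | 50 / 40 | 60.4 / 24.5 / 15.1 | same |

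**Reading the table.** With equal groups the two rules are identical. At a common rate, one extra subject already tilts the count. Where the smaller group is truly better (50% against 40%), expected counts explain the pattern: 8 × 0.5 = 4.0 against 10 × 0.4 = 4.0 is close to a coin toss, and against 11 × 0.4 = 4.4 the worse dose is ahead.

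**Range.** For 8 vs 11 at a common rate, the larger group has the higher count 51.9% of the time against 26.2% at a rate of 20%, and 79.0% against 9.6% at a rate of 70%.

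**Sensitivity to what counts as comparable.** If a difference of one subject or less were called comparable (an assumption), 8 vs 11 at 50% / 40% gives 51% comparable, 30% favouring the larger group and 19% favouring the smaller.

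**The case against.** The strongest reply is that the wording is loose rather than a working rule. What is compared is efficacy, and the number is only how it is read. SAP section 6.1.1 specifies the responder table with both counts and percentages, although that is version 2.0 and the interim used version 1. The DMC includes an independent statistician, who would be expected to notice denominators. The charter may define a rate. None of this can be confirmed from the documents supplied, and section 15.10 itself still states a count. So it softens the point without removing it.

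A second reply concerns size, and it stands in part. The planned cohorts are symmetric, and 8 vs 11 puts one at its floor and the other at the even-split figure. At 10 vs 11 the better dose still leads on counts. The calculation also treats a one-subject lead as decisive, whereas comparable results go to Design 3, safety must also be satisfied, and the Steering Committee decides on a DMC recommendation. The percentages therefore describe the efficacy input, not the probability of a wrong design.

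A reader might go further and infer that the interim could not assess efficacy, because placebo response is absent from the efficacy criterion and every design continues AP1189. The documents do not support that. SAP section 3.7 says the interim was done "in order to assess the safety and efficacy of the investigational product before proceeding to Part 2", and the DMC received CDAI tables by treatment, so placebo response was in front of it. Having no futility rule is a design choice in a small phase IIa study. Whether the charter called for a placebo comparison cannot be checked.

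**Conclusion.** The point holds for section 15.10 as written: if the evaluable 50 mg and 100 mg groups differ in size, the efficacy criterion favours the larger one regardless of effect. The bias is zero at equal sizes, modest at a difference of one, and at 8 vs 11 large enough to favour the worse dose (48% against 34%) where proportions would favour the better one (68% against 32%). This rests on assumed responder rates, on assumed imbalances that the text permits but does not predict, and on treating any lead as higher.

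It would be tempting to conclude that group size determined the actual Part 2 choice. The documents give neither the Part 1 group sizes nor the responder numbers, so that cannot be said.

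**What to change.** In section 15.10, for all three designs, replace the count of subjects with a reduced clinical score by: *the proportion of subjects with a week-4 CDAI in the group who change from CDAI > 22 to CDAI ≤ 22 at week 4*. Align the DMC charter with it. This also settles which reduction in clinical score is meant.

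Because the interim has been performed, the rule actually applied should not be rewritten retrospectively without saying so. The study report should give the numerators, denominators and percentages for 50 mg, 100 mg and placebo behind the Part 2 choice, and state whether counts and proportions would have led to the same design.

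The cost is wording in 15.10 and the charter plus a short table in the report; no new data are needed. One small downside is that exact ties become rarer when groups differ in size, so the judgement of comparable efficacy rests more on the DMC.

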15.11 Stopping Rules

In case of occurrence of a serious medical event (e.g., stroke, convulsion, etc.) or any SAE considered as related to the study drug, the DMC could decide to put the study on hold to unblind the study. After that, depending on the results of the unblinding, the study could either be stopped or continued.

16 STUDY POPULATION

The study population will consist of subjects with severe active RA, defined as CDAI > 22, who are about to begin up-titration with MTX.

16.1 Subject Selection Criteria

The study can fulfill its objectives only if appropriate subjects are enrolled. The following eligibility criteria are designed to select subjects for whom protocol treatment is considered appropriate. All relevant medical and non-medical conditions should be taken into consideration when deciding whether this protocol is suitable for a subject.

16.2 Inclusion Criteria

Subject eligibility should be reviewed and documented by an appropriately qualified member of the investigator's study team before subjects are included in the study. The following are requirements for entry into the study.

- 1. Written informed consent has been obtained prior to initiating any study specific procedures
- 2. Male and female subjects, 18 to 85 years of age
- 3. Confirmed diagnosis of RA according to the 2010 ACR/EULAR RA classification criteria
- 4. Arthritis with joint swelling and tenderness of a minimum of three joints out of 68 joints tested
- 5. Candidate for MTX treatment
- 6. Is about to begin treatment with MTX
- 7. Tested positive for anti-CCP or RF
- 8. Severe active RA (CDAI > 22) at screening and baseline
- 9. Negative QFG-IT (Mantoux test can be used if QFG-IT is not possible)
- 10. Subjects should be able to complete (read and write) the PRO questionnaires
- 11. Females of child-bearing potential may only participate if using reliable means of contraception (for detailed information see section 17.8) or are post-menopausal (menstrual periods stopped at least 12

Protocol Code Number: SynAct-CS002

months ahead of the enrolment in the trial). Surgically sterilized women at least 6 months prior to screening

12. Females of childbearing potential must have a negative pregnancy test at screening and baseline.

16.3 Exclusion Criteria

Subjects meeting any of the following criteria are not eligible for participation in the study:

- 1. Participation in any other study involving investigational drug(s) within 4 weeks prior to study entry
- 2. Major surgery (including joint operation) within 8 weeks prior to screening or planned surgery within 1 month following randomization
- 3. Rheumatic autoimmune disease other than RA, including SLE, MCTD, scleroderma, polymyositis, or significant systemic involvement secondary to RA (e.g., vasculitis, pulmonary fibrosis or Felty's syndrome). Sjögren syndrome with RA is allowable
- 4. Functional class IV as defined by the ACR Criteria for Classification of Functional Status in RA or wheelchair/bedbound
- 5. Prior history of or current inflammatory joint disease other than RA (e.g., gout, reactive arthritis, psoriatic arthritis, seronegative spondyloarthropathy, Lyme disease)
- 6. Subjects with fibromyalgia
- 7. Initiation or change in dose for NSAIDs (including low-dose aspirin and COX-2 inhibitors) within 2 weeks prior to dosing with the IMP
- 8. Corticosteroids are prohibited within 2 weeks prior to screening (and during the entire treatment period and until the final visit (Visit 7)
- 9. Evidence of serious uncontrolled concomitant cardiovascular, nervous system, pulmonary (including obstructive pulmonary disease), renal, hepatic, endocrine (including uncontrolled diabetes mellitus), or gastrointestinal disease
- 10. Have prior renal transplant, current renal dialysis, or severe renal insufficiency (determined by a derived glomerular filtration rate (GFR) using Cockcroft Gault formula of ≤30 ml/min/1,73m² calculated by the local lab)
- 11. Uncontrolled disease states, such as asthma, psoriasis, or inflammatory bowel disease where flares are commonly treated with oral or parenteral corticosteroids
- 12. Evidence of active malignant disease (except basal cell carcinoma of the skin that has been excised and cured)
- 13. Pregnant women or nursing (breastfeeding) mothers
- 14. History of alcohol, drug, or chemical abuse within the 6 months prior to screening
- 15. Neuropathies or other painful conditions that might interfere with pain evaluation
- 16. Body weight of >150 kg.

EXCLUSION CRITERIA 17-20 ONLY APPLY FOR SUBJECTS IN NORWAY:

- 17. Evidence of moderate and/or severe organ dysfunction
- 18. Abnormal chest x-ray (as per the discretion of the investigator)
- 19. Evidence of positive hepatitis serology
- 20. Evidence of peptic ulcer disease

Protocol Code Number: SynAct-CS002

